9.5 Study Schedule of Assessments

In the evening of each day the subject should rate their pain using the provided scale and record their rating in the eDiary. Refer to Table 1 Schedule of Assessments.

Table 1. Schedule of Assessments

Assessments	Screening/Baseline (Day 0)	Day 1 - 14	Research Extension (if applicable) Day 15 – 30
Inclusion/Exclusion Criteria	X		
Demographics	X		
Surgical Date	X		
Pain Assessment	X	X	X
Self-reported Pre-Existing Conditions*	X*		
OrthoCor Active System/SOC Intervention Use		X	X
Device Information	X		
OrthoPod Information	X	X	X
Concomitant Pain Medication Use	X	X	X
Adverse Event, related to the test device		X	X
Pregnancy test for WOCBP	X		

* Information to be collected if available

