10.0 ADVERSE EVENTS

Adverse events (AEs) may occur during the study.

Each adverse event will be recorded in the corresponding subject's eDiary. Each adverse event will be assessed by the Investigator as to its relationship and level of relatedness to the investigational device and/or assessment. In addition, the Investigator will identify the date of onset, severity, and duration of the AE. All adverse events will be monitored until they are adequately resolved or explained. If an AE continues after the evaluation, the Sponsor and Investigator should discuss the need and/or methods for continued surveillance of the event.

The Investigator must submit to the Sponsor a report of any Serious Adverse Event (SAE), Serious Adverse Device Effect (SADE) or Unanticipated Adverse Device Effect (UADE) within 24 hours of knowledge of the event.

Sponsor Contact: [name]
 [contact]
 Email: [contact]

In addition, the Investigator will report adverse events to the reviewing IRB (as applicable) according to the local reporting requirements.

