10.1 Adverse Event Definitions

Adverse Event

An adverse event is any undesirable clinical occurrence in a subject whether it is considered to be device-related or not.

Serious Adverse Event

An adverse event is considered "serious" if, in the view of either the Investigator or Sponsor, it results in any of the following outcomes:

- Death
- Life-threatening
- Hospitalization (initial or prolonged)
- Disability or permanent change
- Congenital Anomaly/Birth Defect
- Required Intervention to Prevent Permanent Impairment or Damage
- Other Serious (Important Medical Events)

Anticipated Adverse Events include those that are reasonably expected to occur in association with the use of OrthoCor Active System (see Appendix B).

Unanticipated Adverse Device Effects (UADE)

Any serious adverse effect on health or safety, any life-threatening problem or death caused by, or associated with a device, if that effect, problem, or death was not previously identified in nature, severity, or degree of incidence in the investigational plan or application (including a supplementary plan or application), or any other unanticipated serious problem associated with a device that relates to the rights, safety, or welfare of subjects (21CFR812.3).

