10.2 Adverse Event Reporting

Adverse events occurring after the baseline assessment but after the study product use will be documented on the appropriate AE report form. All adverse events will be recorded from day 1 until a subject's participation in the trial is considered complete, i.e., at screen failure, completion of study participation (if applicable), subject's demise, or when a subject is discontinued / withdrawn.

It is the responsibility of the Investigators to inform their IRB of adverse events as required by their local IRB procedures.

Anticipated observations related to the study procedure will be tabulated but will not be categorized as adverse events unless they require mitigation by the treating physician or are greater in severity, duration or degree of incidence than anticipated.

Investigators must notify Caerus Corporation (or designee) within 72 hours of discovering any Unanticipated Adverse Device Events (UADE). Investigators are required to submit a report of a UADE to the reviewing IRB as soon as possible, but in no event later than 10

working days after the Investigator first learns of the event. UADEs must be documented as appropriate in the eDiary.

The Sponsor's evaluation of the UADE must be reported to the FDA, all reviewing IRBs, and participating Investigators within 10 working days of knowledge of the event by the Sponsor. All UADE will be reported to the FDA according to regulatory reporting requirements found in CFR 812.46.

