11.6 Safety

All adverse events for subjects in the safety population will be reported.

- Serious Adverse Events
- Non-serious Adverse Events Device Related Adverse Event
- Device Related Serious Adverse Events

Results will include the number of subjects experiencing each type of event as well as the number of events.

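### Table 1 schedules only device-related adverse events, while Protocol 10.0 to 10.2 and 17.3 require all of them to be recorded; the two must be reconciled

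*Protocol*

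**What the plan says.** The schedule in Protocol 9.5 has one adverse event row, "Adverse Event, related to the test device", marked for Days 1–14 and for the research extension. No other row covers adverse events, and the list of data to be collected in Protocol 9.3 does not mention them.

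The adverse event sections are wider:

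- Protocol 10.0: "Each adverse event will be recorded in the corresponding subject's eDiary". Relatedness is a separate step: "Each adverse event will be assessed by the Investigator as to its relationship and level of relatedness to the investigational device and/or assessment".
- Protocol 10.1: an adverse event is "any undesirable clinical occurrence in a subject whether it is considered to be device-related or not".
- Protocol 10.2: "All adverse events will be recorded from day 1 until a subject's participation in the trial is considered complete". One narrow exception is made for anticipated observations from the study procedure, which are tabulated but not classed as adverse events unless stated conditions are met.
- Protocol 17.3: the site investigator is to monitor and report all adverse events.
- Protocol 11.6: "All adverse events for subjects in the safety population will be reported", with device-related events among the listed categories. SAP 12.8 repeats this.

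SAP 11.2 limits the safety population to subjects who have been treated with the active device.

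**The concern.** Table 1 and Section 10 give different answers to a basic question: does an event thought unrelated to the device get recorded? Under Section 10 it does, and the Investigator then judges it. Under Table 1 it is never scheduled for capture, so someone must judge relatedness before any record exists. The trial is open label, so that judgement is made knowing the assignment.

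Several features of this trial raise the stakes. Protocol 9.0 describes a single on-site visit followed by remote data collection, so no later visit is scheduled at which staff would ask about events. Adverse events are the primary safety endpoint, and Protocol 11.2 makes the descriptive adverse event table the whole of the safety reporting. The sponsor's trend monitoring (Protocol 12.3) and the discontinuation ground based on unexpectedly frequent events (Protocol 16.0) both depend on complete capture.

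**Working it through.** No formula applies. The claim concerns which events are collected and uses no rate, effect size or error level. The check sets the rules side by side for each kind of event.

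| Event | Table 1 row | Protocol 10.0–10.2 and 17.3 | Planned tables (Protocol 11.6, SAP 12.8, with SAP 11.2) |
|---|---|---|---|
| Device subject, non-serious, related | Captured | Recorded | Reported |
| Device subject, non-serious, unrelated | Not scheduled | Recorded | Reported |
| SOC subject, Days 1–14, non-serious | None can qualify | Recorded | Reported only if the subject later uses the device |
| SOC subject crossed over, extension, non-serious, related | Captured | Recorded | Reported |
| SOC subject crossed over, extension, non-serious, unrelated | Not scheduled | Recorded | Reported |
| Serious event, either arm | In the row only if related | Recorded; sent to the sponsor within 24 hours whatever the relatedness | Reported if the subject is in the safety population |

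1. **Device subjects.** Row 2 is a direct conflict. Section 10 has the event recorded and Protocol 11.6 has it reported, but Table 1 does not schedule it. Device-related events are a category within a report of all events, and that report is incomplete if unrelated events never enter the database.

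2. **SOC subjects.** They have no test device in Days 1–14, so no event of theirs can meet the Table 1 wording in that period. This touches up to 50 of up to 100 subjects: 50 / 100 = half of planned enrolment. In the optional extension, those who cross over can have device-related events. Protocol 10.3 does foresee events associated with standard of care.

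3. **Serious events.** Protocol 10.0 and 17.3 require a report within 24 hours, with no limit by arm or relatedness. The exposure is therefore mainly to non-serious events.

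4. **Which text governs.** Neither document gives an order of precedence, and Protocol 9.3 does not help because it omits adverse events.

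5. **Size.** The count of events lost would be the number of affected subjects, times the rate of non-serious events that Table 1 leaves out, times the share of sites or diary screens that follow Table 1. The documents give neither the rate nor the share, so no figure can be put on it.

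**The case against.** The strongest reply is that the operative text is clear. Sections 10.0, 10.1, 10.2 and 17.3 all point the same way, site initiation covers the protocol and the reporting requirements (Protocol 15.3), and nothing says that sites or the eDiary build work from Table 1. On this view one loosely worded row is outvoted. That stands as a limit: the harm is conditional on Table 1 being followed. It does not remove the contradiction, because Table 1 is the only place in Section 9 where adverse event collection is scheduled.

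Several stronger readings are tempting, and the documents do not support them:

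- A reader might infer that SOC subjects will contribute no adverse events. That would require sites to disregard Section 10 and 17.3 altogether, and serious events would still be reportable.
- A reader might infer that subjects judge relatedness themselves, because events go into their eDiary. Protocol 10.0 gives that judgement to the Investigator, and 10.2 also refers to an adverse event report form. Who would apply the Table 1 filter is not stated.
- A reader might infer that unrecorded events are irrecoverable. Monitors review medical records and clinic charts (Protocol 15.5), so some could be found, although mild events at home may leave no trace there.
- A reader might count how many planned table categories become incomplete. The list in Protocol 11.6 and SAP 12.8 runs two labels together in one bullet, so the number of categories is not secure.
- A reader might blame Table 1 for the absence of SOC harms from the safety tables. SAP 11.2 already excludes SOC subjects who never use the device, whatever Table 1 says.

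Safety reporting is descriptive, so no planned test or comparison changes. The exception in 10.2 also means that the all-events rule is not quite absolute.

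**Conclusion.** The inconsistency is real and sits in the current text. Table 1 restricts adverse event collection to device-related events, against Protocol 10.0 to 10.2 and 17.3. For device subjects it also conflicts with the all-events reporting in Protocol 11.6 and SAP 12.8.

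If Table 1 is followed, two consequences hold: non-serious events thought unrelated may go unrecorded in up to 50 device subjects, and up to 50 SOC subjects have no qualifying non-serious event in Days 1–14. The first leaves the primary safety endpoint data incomplete. Both rest on the assumption that sites or the eDiary use the Table 1 wording, which the documents neither confirm nor rule out. The number of events at risk is unknown. The point should be corrected because the rule as written gives an incomplete safety record and the correction is small.

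**What to change.** Reword the Table 1 row to *Adverse events (all, both arms; relatedness assessed by the Investigator)* for Days 1–14 and the extension, and check that the eDiary prompts and the adverse event form match it.

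Two further passages should be reconciled in the same amendment:

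- Protocol 10.2 opens by tying documentation to the period after study product use, then says recording starts on day 1. The starting point should be stated so that it is also clear for SOC subjects.
- SAP 11.2 should say how events in SOC subjects who never use the device will be tabulated, for example through a safety population covering both arms and summarised by treatment received. Otherwise the row change restores collection of SOC events without bringing them into any planned table.

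The cost is one table row, a diary and form check, one clarified sentence in 10.2 and one population definition in the SAP. No collection is added beyond what Section 10 already requires; the SOC tabulation is a small addition to the reporting.

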10.0 ADVERSE EVENTS

Adverse events (AEs) may occur during the study.

Each adverse event will be recorded in the corresponding subject's eDiary. Each adverse event will be assessed by the Investigator as to its relationship and level of relatedness to the investigational device and/or assessment. In addition, the Investigator will identify the date of onset, severity, and duration of the AE. All adverse events will be monitored until they are adequately resolved or explained. If an AE continues after the evaluation, the Sponsor and Investigator should discuss the need and/or methods for continued surveillance of the event.

The Investigator must submit to the Sponsor a report of any Serious Adverse Event (SAE), Serious Adverse Device Effect (SADE) or Unanticipated Adverse Device Effect (UADE) within 24 hours of knowledge of the event.

Sponsor Contact: [name]
 [contact]
 Email: [contact]

In addition, the Investigator will report adverse events to the reviewing IRB (as applicable) according to the local reporting requirements.

10.1 Adverse Event Definitions

Adverse Event

An adverse event is any undesirable clinical occurrence in a subject whether it is considered to be device-related or not.

Serious Adverse Event

An adverse event is considered "serious" if, in the view of either the Investigator or Sponsor, it results in any of the following outcomes:

- Death
- Life-threatening
- Hospitalization (initial or prolonged)
- Disability or permanent change
- Congenital Anomaly/Birth Defect
- Required Intervention to Prevent Permanent Impairment or Damage
- Other Serious (Important Medical Events)

Anticipated Adverse Events include those that are reasonably expected to occur in association with the use of OrthoCor Active System (see Appendix B).

Unanticipated Adverse Device Effects (UADE)

Any serious adverse effect on health or safety, any life-threatening problem or death caused by, or associated with a device, if that effect, problem, or death was not previously identified in nature, severity, or degree of incidence in the investigational plan or application (including a supplementary plan or application), or any other unanticipated serious problem associated with a device that relates to the rights, safety, or welfare of subjects (21CFR812.3).

10.2 Adverse Event Reporting

Adverse events occurring after the baseline assessment but after the study product use will be documented on the appropriate AE report form. All adverse events will be recorded from day 1 until a subject's participation in the trial is considered complete, i.e., at screen failure, completion of study participation (if applicable), subject's demise, or when a subject is discontinued / withdrawn.

It is the responsibility of the Investigators to inform their IRB of adverse events as required by their local IRB procedures.

Anticipated observations related to the study procedure will be tabulated but will not be categorized as adverse events unless they require mitigation by the treating physician or are greater in severity, duration or degree of incidence than anticipated.

Investigators must notify Caerus Corporation (or designee) within 72 hours of discovering any Unanticipated Adverse Device Events (UADE). Investigators are required to submit a report of a UADE to the reviewing IRB as soon as possible, but in no event later than 10

working days after the Investigator first learns of the event. UADEs must be documented as appropriate in the eDiary.

The Sponsor's evaluation of the UADE must be reported to the FDA, all reviewing IRBs, and participating Investigators within 10 working days of knowledge of the event by the Sponsor. All UADE will be reported to the FDA according to regulatory reporting requirements found in CFR 812.46.

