11.2 Safety Variables

This is a non-significant risk study. Because no additional procedures are required to perform the investigational test, safety will be monitored via the reported Adverse Events in this study. The descriptive table of Adverse Events will be the extent of safety reporting.

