12.0 RISK – BENEFIT ASSESSMENT

12.1 Potential Risks

There are no known risks associated with the use of the OrthoCor Active System other than the normal minor risks/discomforts associated with the OrthoPods, which could result in localized burns and/or skin sensitivity and irritation.

Potential risks associated with the OrthoCor Active System do not differ from those of the commonly used non-invasive in-vitro devices that provide RF and heat treatment to localized area(s).

The following are adverse events or side effects that may occur as a result of the OrthoCor Active System assessment:

- a) Loss of confidentiality due to study participation.

Subjects will be monitored closely as part of this study for the detection of symptoms to allow for early treatment or intervention, if necessary.

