20.0 APPENDICES

APPENDIX A. OrthoCor Active System - INSTRUCTIONS FOR USE (IFU)

APPENDIX B. ADVERSE EVENTS

APPENDIX A.**OrthoCor Active System - INSTRUCTIONS FOR USE (IFU)**

APPENDIX B.**Adverse Events**

The following adverse events are unexpected but may occur with use of OrthoCor Active System:

- Patient injury during use such as skin irritation or burns.

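### Protocol 10.2's exclusion of anticipated observations, together with Appendix B's conflicting label, may leave untreated skin irritation or minor burns out of the safety result

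*Protocol*

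**What the plan says.** - **Definition (Protocol 10.1).** "An adverse event is any undesirable clinical occurrence in a subject whether it is considered to be device-related or not". Anticipated events are not excluded.
- **Anticipated events (Protocol 10.1).** "Anticipated Adverse Events include those that are reasonably expected to occur in association with the use of OrthoCor Active System (see Appendix B"). Section 10.3 also describes Appendix B as the list of expected events.
- **Exclusion (Protocol 10.2).** Anticipated procedure-related observations "will be tabulated but will not be categorized as adverse events unless they require mitigation by the treating physician". The sentence then adds a second condition: "or are greater in severity, duration or degree of incidence than anticipated". Either condition brings the observation back into the adverse event category.
- **Appendix B.** "The following adverse events are unexpected but may occur with use of OrthoCor Active System". One entry follows: injury in the form of skin irritation or burns. No grade, duration or rate is attached.
- **Known risks (Protocol 12.1).** The OrthoPods could cause "localized burns and/or skin sensitivity and irritation", which the section presents as normal and minor.
- **Endpoint and reporting.** The primary safety endpoint is adverse events reported with the device after 2 weeks (Protocol synopsis; SAP section 5). Protocol 11.2 adds: "The descriptive table of Adverse Events will be the extent of safety reporting". SAP 12.3 says the same. Protocol 11.6 and SAP 12.8 list only categories of adverse event, with no output for observations that were tabulated but not classed as such.

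**The concern.** The only physical device harms that the protocol names are skin irritation or sensitivity and burns. If these count as anticipated, 10.2 can keep the mild, untreated ones out of the adverse event category, and so out of the only safety table. If they count as unexpected, as Appendix B labels them, the exclusion does not touch them. The protocol supports both readings, so the count may depend on which section a site follows.

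Misapplying the exclusion can only lower the device's count. The schedule of assessments (Protocol 9.5, Table 1) collects adverse events related to the test device, and the SAP 11.2 safety population is device-treated subjects only. Device-related events are therefore the core of the safety result. Protocol 18.4 says that the results may support an FDA submission.

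**Working it through.** The documents give no figure to reproduce: no anticipated rate, no severity grade and no safety threshold. The check is a comparison of passages.

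**1. Classify one event under each passage.** Take mild skin irritation under the brace that needs no physician treatment.

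| Passage followed | Status | In the adverse event table? |
|---|---|---|
| Protocol 10.1 definition | Undesirable occurrence | Yes |
| Protocol 10.2, with 10.1 and 10.3 treating Appendix B as the anticipated list | Anticipated, not mitigated | No, unless worse than anticipated |
| Protocol 10.2, with Appendix B's own label | Unexpected, so outside the exclusion | Yes |

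The same event has two possible outcomes.

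**2. Can the second condition be applied?** It needs an anticipated level of severity, duration or incidence.
- Incidence: not stated in 10.1, 10.3, 12.1 or Appendix B.
- Duration: not stated.
- Severity: 12.1 gives only a qualitative level (minor; localized burns).

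A clearly severe burn would pass on severity. A mild event has no benchmark for duration or incidence.

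**3. Does the exclusion reach device effects?** The wording in 10.2 concerns the study procedure, not the device by name. Protocol 11.2 says that no additional procedures are required, and SAP 12.3 says that none are. In Table 1, apart from device or SOC use, only the pregnancy test resembles a procedure; the rest is data collection. Device use is what remains for the rule to cover. This is a strong inference, not explicit text.

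**4. Where do excluded observations go?** Section 10.2 has them tabulated, so they are recorded. No table or listing in Protocol 11.2 or 11.6, or in SAP 12.3 or 12.8, is assigned to them.

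**5. Scale, by assumption only.** Let n = 50 (the maximum device arm), p = true incidence of mild skin events and c = share of affected subjects kept out by the exclusion. Both p and c are assumed. Then the expected number affected is np, the expected number in the table is np(1 − c), and the chance of none in the table is [1 − p(1 − c)]^50, with subjects independent.

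| p | Affected | In table, c = 25% | Chance of none | In table, c = 50% | Chance of none |
|---|---|---|---|---|---|
| 2% | 1 | 0.75 | 47% | 0.5 | 60% |
| 5% | 2.5 | 1.875 | 15% | 1.25 | 28% |
| 10% | 5 | 3.75 | 2.0% | 2.5 | 7.7% |
| 20% | 10 | 7.5 | 0.03% | 5 | 0.5% |

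For example, with p = 10% and c = 50%: 50 × 0.10 × 0.50 = 2.5, and 0.95^50 = 0.077. At c = 100% the table shows none at any p.

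**The case against.** The case for the plan has several parts.

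- **Different terms.** Section 10.2 speaks of observations related to the study procedure; 10.1 speaks of anticipated adverse events with device use, and still calls those adverse events. On that reading 10.2 never covered device effects. This stands as a possible reading, but step 3 shows how little else the rule could cover, and nothing tells a site to read it so.
- **Two ways back in.** A reader might infer that device harms are dropped unless treated. The text does not say that: events that exceed what was anticipated also return. This stands, and a severe burn would be counted. For mild events the condition has almost nothing to compare with.
- **Literal label.** A reader might take the listed harms to be simply the anticipated ones. Appendix B calls them unexpected, and read literally that removes them from the exclusion. What the documents support is a contradiction, not a settled status.
- **Nothing is lost.** The observations are tabulated, and Protocol 9.3 tells device users to contact the site about unusual sensations or discomfort. So it cannot be said that all mild skin events disappear. The gap is in classification and in the lack of an assigned output.
- **No test to distort.** Safety is descriptive. This is true, but the descriptive count is itself the primary safety result.

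**Conclusion.** The point holds in a limited form. Section 10.2 conflicts with the unrestricted definition in 10.1, and Appendix B's label conflicts with 10.1 and 10.3. As written, untreated skin irritation or minor burns may be left out of the primary safety result, which could bias the device count downwards. This rests on reading the study procedure to include device use, and on sites following 10.1 and 10.3 rather than Appendix B's heading.

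The size cannot be estimated from the documents. The scale table depends wholly on assumed rates and shares, and an empty adverse event table is likely only if events are rare or nearly all are excluded.

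A reader might also infer that the Appendix B label decides whether a serious burn is an unanticipated adverse device effect. The 10.1 definition does not support this: it asks whether the nature, severity or incidence of the effect was previously identified in the plan, and burns are named in both 12.1 and Appendix B whatever the heading.

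**What to change.** - **Protocol 10.2.** State that undesirable device-related events, including skin irritation and burns, are recorded and reported as adverse events whatever their anticipated status and whether or not they need treatment. Limit the exclusion to study procedures that do not involve the device.
- **Protocol 10.1, 10.3, 12.1 and Appendix B.** Reconcile these in the same amendment, so that the Appendix B label agrees with 10.1 and 10.3. Do not relabel Appendix B alone: without the 10.2 change, that would place burns and irritation more firmly inside the exclusion.
- **SAP 12.3 and 12.8.** State that these events appear in the adverse event table.

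The cost is protocol and SAP wording plus a table line, since 10.2 already has the observations tabulated. The downside is a higher reported adverse event count for the device.
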